### 6.9.2.3 Other Endpoints

The same descriptive statistics and ANCOVA model as the primary efficacy endpoint will be applied to metabolic marker endpoints, biomarker endpoints, and other secondary outcome measures will be summarized and analyzed in the same manner as the primary efficacy endpoint. LOCF will be used in place of multiple imputation.

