5.2.2 Secondary Endpoint(s)

The secondary endpoint of the study is time to remission (TTR). TTR is defined as time in weeks from randomization to liver function remission as defined as two consecutive ALT values within normal range (< 20 U/mL for woman and < 30 U/L for men) or 20% reduction from the baseline during study period.

- TTR rate in ALT at the end of the treatment period.
- Assess the pharmacokinetic profile of JKB-121 in NASH

- Change on metabolic markers associated with NASH
- Change in liver enzymes (serum ALT) over 24 weeks.
- Change of NASH related biomarkers such as adiponectin, leptin, ghrelin, TNF-alpha, TGF-beta, hyaluronic acid and MMP-2.

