13.2 General Statistical Methodology

Prior to database lock, a final detailed Statistical Analysis Plan (SAP) will be available. Results, when available, will be summarized into tabulations, case listings, plots, and histograms for comparison.

Three major study populations are planned, modified intent-to-treat (met) population, per protocol (PP), and safety populations.

Baseline variables will be ascertained for conformity among all stratification factors. All baseline analysis will be based on the met population. In the met population, the subjects will be counted in the treatment group to which they were randomized, as long as they received at least one dose of study medication and have at least one return visit.

The safety analysis will be based on the safety population. In the safety population, subjects will be counted in the group in which they were treated. To assess the robustness of the study outcomes, a sensitivity analysis will be performed on all pertinent major efficacy variables. The sensitivity analysis will include and exclude patients with major study deviations and early withdrawals to assess the impact on the study endpoints.

The criteria may be amended prior to unbinding of the treatment assignment for the analysis of data. Reasons for changes may include study conduct changes, protocol amendments, or changes in the appropriateness of the criteria, which may be assessed based on review of blinded data.

For all analyses, all missing values due to patient early termination from the study will be not imputed.

For each patient, the Baseline values will be defined as those values recorded at Day 1 prior to dosing or Screening, as appropriate.

All hypotheses will be tested for statistical significance with two-tailed p-values. Results of all tests will be considered statistically significant if their p-value is less than or equal to 0.05, except for results of the tests for interaction will be considered statistically significant if the p-value is less than or equal to 0.10.

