13.4.1.2. Secondary Efficacy Endpoint

The secondary endpoints of this study are:

- Time to remission (TTR) is defined as time, in weeks, from randomization to liver function remission as defined as two consecutive ALT values within normal range (< 40 IU/mL) during study period. The Cox proportional hazard model with treatment and diabetes status as factors, will be used.
 - ALT changes from baseline. The statistical analysis will be the same as the one used for the primary efficacy endpoint
 - Changes in metabolic markers and NASH related biomarkers

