### 5.3 Other Efficacy Endpoints

- Metabolic Marker Endpoints
  - Body mass index (BMI) at each scheduled visit and the corresponding changes from baseline.
  - HbA1c and the homeostatic model assessment of insulin resistance (HOMA-IR) at each scheduled visit and the corresponding changes from baseline.
  - Serum lipid profile (total cholesterol, triglycerides, low density lipoprotein [LDL], and high density lipoprotein [HDL]) at each scheduled visit and the corresponding changes from baseline.
- Biomarker Endpoints
  - Biomarkers such as adiponectin, leptin, ghrelin, TNF-alpha, TGF-beta, hyaluronic acid and MMP-2 at each scheduled visit and the corresponding changes from baseline.
- Exploratory Outcome Measures
  - Mean serum concentrations of lipopolysaccharide (LPS), c-reactive protein (CRP), cytokeratin (CK)-18 fragments, proinsulin c-peptide, glucagon-like polypeptide (GLP-1) and adiponectin.
  - Relative levels of inflammatory cytokines, interferon gamma (IFN- $\gamma$ ), and TNF-alpha
  - Relative levels of regulatory T cells in the peripheral blood mononuclear cells (PBMC) samples including CD4, CD8, CD 25, Fox P3, NKT, and CD62 T cells.

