### 6.9.2.2 Liver Function

The same descriptive statistics, ANCOVA model, and multiple imputation as the primary efficacy endpoint will be applied to serum aspartate aminotransferase (AST), ALT, and gamma-glutamyl transpeptidase (GGT) at each scheduled visit for the Full Analysis Set Population and the mITT Population.

As a sensitivity analysis, the change from baseline in AST, ALT, and GGT will be analyzed using a mixed-model repeated-measures (MMRM) ANCOVA model for the Full Analysis Set Population, implemented using SAS® Proc Mixed. The factors in the model will be diabetes stratum, treatment group, baseline value, visit, and the treatment group by visit interactions. An unstructured covariance matrix will be used (TYPE=UN). No imputation will be performed. The sample SAS code can be found below:

```
*****
Note:
  USUBJID = unique subject identifier
  TREATMENT = 0, (placebo), 1 (JKB-121 5 mg), 2 (JKB-121 10 mg)
  DIABSTAT = nondiabetic, diabetic
  VISIT = visit
  BASE = baseline value
  CHG = change from baseline to the specified visit
*****;
proc mixed;
  class USUBJID DIABSTAT TREATMENT BASE VISIT;
  model CHG = DIABSTAT TREATMENT BASE VISIT TREATMENT*VISIT;
  Repeated VISIT / TYPE=UN sub=USUBJID;
  lsmeans VISIT*TREATMENT / cl pdiff slice=VISIT;
run;
```

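### Secondary metabolic markers and NASH biomarkers are imputed by LOCF, against the protocol's no-imputation rule and without the MI or MMRM used for the other efficacy endpoints

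*SAP*

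**What the plan says.** SAP 6.9.2.3 sets the model: "The same descriptive statistics and ANCOVA model as the primary efficacy endpoint will be applied to metabolic marker endpoints, biomarker endpoints". It then sets the missing-data rule: "LOCF will be used in place of multiple imputation". No reason is given, and no sensitivity analysis is planned for these endpoints.

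The protocol treats them as secondary. Section 5.2.2 lists "Change on metabolic markers associated with NASH" and "Change of NASH related biomarkers such as adiponectin, leptin, ghrelin, TNF-alpha, TGF-beta, hyaluronic acid and MMP-2", and section 13.4.1.2 repeats "Changes in metabolic markers and NASH related biomarkers". The SAP keeps both among its secondary objectives (3.2) but places the endpoints in section 5.3, "Other Efficacy Endpoints".

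On missing data, Protocol 13.2 states: "For all analyses, all missing values due to patient early termination from the study will be not imputed". SAP 6.2 allows LOCF or multiple imputation where specified. SAP 6.9.1 specifies multiple imputation for MRI fat. SAP 6.9.2.2 applies it to AST, ALT and GGT, and adds that, as a sensitivity analysis without imputation, "the change from baseline in AST, ALT, and GGT will be analyzed using a mixed-model repeated-measures (MMRM) ANCOVA model".

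**The concern.** Two things are wrong. First, the documents conflict: the protocol forbids imputation after early termination, and the SAP imputes. Second, the SAP handles missing data in one way for MRI fat and liver enzymes and in a weaker way for these secondary endpoints, and does not say why.

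LOCF assumes that a subject's value stays where it was at the last visit. If the group mean is still moving, carried values fall short of Week 24. The arm with more dropout then appears to have changed less, whether or not the drug did anything. Choosing a dose for later studies is a secondary objective, so dropout related to dose could distort a comparison that readers will use. Withdrawn subjects are not replaced, and the sample size makes no allowance for dropout (SAP 4.2 and 6.1).

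The rule is also incomplete. It does not say whether baseline is carried when there is no later value. Nor does it say whether an on-treatment value may be carried into the off-treatment Week 28 visit, where lipids, HbA1c, HOMA-IR and biomarker samples are also collected (Protocol 10.4.5).

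**Working it through.** The documents give no dropout rate, effect size or SD for these endpoints, so there is no planned figure to reproduce. The size of the bias can only be illustrated.

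**Inputs from the documents.** There are 20 subjects per arm. In Protocol Table 10.2.1, lipids, HbA1c and HOMA-IR are measured at Weeks 4, 8, 12, 16, 20 and 24, and the stored serum for biomarkers at Weeks 12 and 24 on treatment.

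**Assumptions.** The mean change is linear to Week 24. Dropout is unrelated to outcome and spread evenly over the intervals between visits. Baseline is carried if nothing later exists.

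**Formula.** Let d be the dropout proportion and f the mean fraction of the Week 24 change reached at the last visit before dropout. The expected LOCF change is (Week 24 mean change) × [(1 − d) + d·f] = (Week 24 mean change) × [1 − d(1 − f)].

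**Carried fraction.**
- Four-weekly markers: the last visit is Week 0, 4, 8, 12, 16 or 20, with mean 10, so f = 10/24 = 0.42.
- Week 12/24 biomarkers: the last visit is Week 0 or 12, with mean 6, so f = 6/24 = 0.25.

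**Unequal dropout, no drug effect, both arms change by D, 25% v 5%.** The spurious difference is (0.25 − 0.05)(1 − f)D.
- Four-weekly: 0.20 × 0.583 = about 0.12D.
- Biomarkers: 0.20 × 0.75 = 0.15D.
- If baseline is not carried, subjects without a later value drop out of the analysis and f becomes 0.5. Dropouts are then 21.7% v 4.2% of those analysed for the four-weekly markers (0.25 × 5/6 ÷ (1 − 0.25/6), and likewise for 5%), giving about 0.09D. For the biomarkers they are 14.3% v 2.6% (0.125/0.875 and 0.025/0.975), giving about 0.06D.
- If D = 0, the difference is 0 under either rule.

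**Equal dropout of 20%, true effect −0.5 SD, placebo flat.**
- Four-weekly: −0.5 × (1 − 0.20 × 0.583) = about −0.44.
- Biomarkers: −0.5 × (1 − 0.20 × 0.75) = about −0.43.

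**Scale.** In simulated trials (ANCOVA, 20 per arm, assumed within-subject correlation 0.6), the standard error of the difference was about 0.25 SD. At D = 0.5 SD, the 25% v 5% illustration gives 0.06 SD (0.12 × 0.5) to 0.075 SD (0.15 × 0.5), roughly a quarter to a third of that standard error. Type I error in that setting was roughly 5% to 6%, rising to roughly 8% to 9% at D = 1 SD. In a harsher case (40% v 10% dropout, D = 1 SD) the spurious difference was 0.18 SD and 0.23 SD, with type I error of 10% and 14%. Under the 3,000-run settings, analysing observed Week 24 values without carry-forward was nearly unbiased (0.00 to 0.01 SD). MMRM itself was not simulated.

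**The case against.** The strongest reply is that little is at stake. The trial is exploratory and makes no multiplicity adjustment, these are not primary endpoints, and discontinuers are asked to complete the end-of-treatment assessments (Protocol 6.3.1, 10.1, 10.4.4 and 10.4.6). Under moderate assumptions the bias is small beside the standard error. All of this stands. It limits severity, but it neither supplies a reason for LOCF nor removes the conflict with Protocol 13.2.

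A reader might also infer more than the documents support:

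- **That unequal dropout always biases LOCF.** It does not. With flat means there is no bias.
- **That a common trend is assured because every visit includes counselling on weight, diet and exercise.** Protocol 3.1 says most patients cannot achieve and keep up the lifestyle change needed, lipid-lowering and antidiabetic drugs must be stable, and recent weight change is an exclusion. A trend is plausible, not established.
- **That LOCF understates the standard error here.** In simulation at 25% v 5% dropout, the mean model standard error and the true sampling SD were 0.252 v 0.258 (four-weekly visits, no change) and 0.250 v 0.251 (Weeks 12/24, D = 0.5 SD). The type I error inflation comes from bias.
- **That the SAP demoted these endpoints to exploratory.** It lists metabolic markers and biomarkers in 5.3 apart from its exploratory measures, and 6.9.2.3 falls under Secondary Endpoints. The status of the biomarkers is mixed in the protocol itself: the synopsis visit schedule calls them exploratory, and adiponectin and TNF-alpha appear on both lists.
- **That the bias reaches 0.20D at 25% v 5%.** For the biomarkers, that needs every dropout to leave before Week 12 and baseline to be carried, which the SAP does not say.

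The conflict with Protocol 13.2 is not peculiar to LOCF: the multiple imputation for MRI fat and liver enzymes departs from the same sentence.

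**Conclusion.** The point holds, at moderate weight. The conflict between SAP 6.9.2.3 and Protocol 13.2, and the unexplained difference from the handling of MRI fat and liver enzymes, are facts of the text and need no assumption.

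The bias is conditional. It needs means that change over time. It then appears with unequal dropout, and with equal dropout when there is a true effect. Its size in this trial is unknown because no dropout rate is given. The figures of 0.12D and 0.15D rest on an assumed 25% v 5% dropout, a linear change, evenly spread dropout unrelated to outcome, and carried baseline. Both are small beside the standard error unless the change or the imbalance in dropout is large. The case for change is that LOCF has no stated advantage here and a better method is already partly specified in the SAP.

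**What to change.** Replace the LOCF sentence in SAP 6.9.2.3 with MMRM on observed data as the main analysis for metabolic markers and NASH biomarkers. Specify:

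- baseline as a continuous covariate. The enzyme code in 6.9.2.2 lists BASE in the CLASS statement, so it must not be copied unchanged;
- on-treatment visits only, named for each endpoint, with Weeks 12 and 24 for the biomarkers and Week 28 summarised separately;
- a fallback covariance structure. An unstructured matrix over six visits has 6 × 7/2 = 21 parameters, with about 60 subjects.

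Keep LOCF at most as a sensitivity analysis, and then state whether baseline is carried. Do not transfer the primary multiple-imputation steps as they stand, because Step 3 averages Weeks 12 and 24 into the endpoint. MMRM is only a sensitivity analysis for the enzymes, so say in a line why it leads here: it imputes nothing and therefore fits Protocol 13.2. Reconcile the SAP with that section explicitly, including the imputation used in 6.9.1 and 6.9.2.2.

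The cost is a short SAP paragraph, adapted code, a missing-at-random assumption and possibly some handling of non-convergence. No data collection changes.

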## 6.10 Pharmacokinetic Analysis

### 6.10.1 Sample Collections for Pharmacokinetic Analysis

Six mL of blood will be collected from fasting (at least 8 hours) subjects on Day 1 prior to dosing, and during Visits 4, 6, and 8 for measurements of the plasma concentrations of

JKB-121. In a subset of volunteers who consent to participate in PK Substudy, blood samples will be collected on Day 1 pre-dose and at each sampling point post-dose for PK evaluation.

From volunteered subjects for intensive PK studies: Blood samples will be obtained on Day 1 prior to 12 hour dosing (predose and at 0.25, 0.5, 0.75, 1.0, 1.5, 2.0, 3.0, 4.0, 6.0, 8.0, 10, 12, and 24 (next day) hours post dose administration in three volunteered subjects from each treatment group (5 mg and 10 mg bid). Additional pre-dose blood sample for trough PK level at Day 1, weeks 8, 16, and 24 will be collected for assessment of steady state PK analysis as well as biomarker study.

### 6.10.2 Pharmacokinetic Variables

The following noncompartmental PK parameters will be calculated from plasma samples prior to the 12 hour dosing collected for the PK Substudy Population if data allows:

- Area under concentration-time (AUC) curve from time 0 to infinity (AUCinf)
- AUC curve from time 0 to time of last quantifiable concentration (AUClast)
- AUC curve from time 0 to 12 hours (AUC12h)
- Minimum post-dose concentration (Cmin)
- Maximum post-dose concentration (Cmax)
- Time of Cmax (Tmax)
- Apparent first-order terminal elimination rate constant calculated by linear regression of the terminal linear portion of the log concentration vs. time curve (Kel)
- Terminal phase elimination half-life (t1/2)
- Clearance (CL/F)
- Volume of Distribution (Vz/F)
- Percent AUC Extrapolated (AUC%extrap)

Parameters Kel, t1/2, and AUCinf will not be presented for those subjects who do not exhibit a terminal elimination phase in their concentration versus time profiles. In order to estimate the constant Kel, linear regression of concentration in logarithm scale vs. time will be performed using at least 3 data points. Uniform weighting will be selected to perform the regression analysis to estimate Kel. The constant Kel will not be assigned if the terminal elimination phase is not linear (as appears in a semi-logarithmic scale), the terminal elimination rate constant indicates a positive slope (Kel < 0), if the Tmax is one of the 3 last data points, or the regression coefficient (R^2) is less than 0.8.

The actual time relative to dosing will be used in the PK parameter calculation. The Linear Up/Log Down method will be used in the computation of all AUC values. The AUClast will

be calculated from 0 hour to the last time point with quantifiable concentration. The AUCinf will be calculated as AUClast + Clast/Kel, where Clast is the last quantifiable plasma concentration.

If one or more non-quantifiable (NQ) values occur in a profile before the first measurable concentration, they will be assigned a value of zero. If a single NQ value occurs between measurable concentrations in a profile, the NQ should generally be omitted (set to missing). NQs which occur after the last measurable concentration will be omitted (set to missing).

### **6.10.3 Pharmacokinetic Summary and Analysis**

PK concentration data will be summarized for each time point using descriptive statistics from the Safety Population and PK Substudy Population (i.e., Mean, SD, Minimum, Maximum, Median, %CV, Geometric Mean, Geometric %CV) by treatment group. Plots of mean concentrations of plasma concentrations (with standard deviation bars) versus nominal time will be generated for each treatment. Individual plasma concentration versus actual time plots will also be provided.

The PK parameters will be summarized by treatment group using the PK Substudy Population. Geometric mean and geometric coefficient of variation (CV%) will be added to the descriptive statistics for Cmin, Cmax, and all AUCs.

Trough (pre-dose) concentrations at Week 8, Week 16, and Week 24 will be summarized by treatment group for the Safety Population. If any trough concentration is NQ, it will be set to zero prior to summarization. Plots of mean trough concentrations (with standard deviation bars) by visit will be generated for each treatment.

The relationship between PK and efficacy may be explored as needed.

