6.1 Duration of the Study

Subjects will be on treatment for up to 24 weeks. Subjects who experience adverse reaction will discontinue study drug but will continue to complete all protocol-specified follow-up visits, assessments and evaluations. They will then continue to be followed up for the remaining duration of the study. Unless otherwise recommended by the Independent Data Review Board (IDRB) or regulatory authorities, the study will continue until it accrues a minimum of 60 subjects complete the study.

Until formal conclusion of the study, subjects, investigators and all site study personnel will be remain blinded as to treatment allocation, except in the event of a medical emergency which necessitates unblinding.

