10. SCHEDULE OF EVENTS

10.1 Tests and Evaluations

No subject may be permitted to undergo any protocol-specified investigations or interventions in this study until they have provided a signed, dated, written informed consent.

All tests and evaluations must be performed prior to that day's administration of study drug treatment. Subjects should undergo all tests and evaluations specified in the protocol, regardless of whether they remain on study drug. Insofar as possible, all blood samples should be collected at approximately the same time of day in each visit, in order to minimize diurnal variation.

The required procedures for patient evaluation at each study visit are outlined in the study. Schedule of Visits and Procedures are in Sections 10.2 and detail items in section 10.3 through 10.4.8. Detailed instructions for specific procedures are presented in Section 11.

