10.3.3 Enrollment Visit (Day 1, Visit 1)

Subjects returning to the clinic for randomization at Day 1 must be in a fasted state for at least 8 hours prior to sample collection prior dosing for this visit, which is a requirement for some of the blood test that will be performed as noted below.

Subjects will be randomized to study drug kit assignment and receive their Subject Identification Number prior to the first dose of study drug being administered. The following will be performed for all subjects who meet the inclusion criteria and not of the exclusion criteria

- Confirm that the subject continues to be eligible for participation
- Record vital signs
- Record weight
- Physical examination
- Hospital Anxiety and Depression Scal and Columbia Suicide Severity Scale Questionnaires.
- Complete blood samples for:
 1. Complete blood count with differential
 2. Blood chemistry including: ALT, AST, albumin, alkaline phosphatase, bicarbonate, BUN, calcium, chloride, creatinine, glucose, LDH, magnesium, phosphorus, potassium, sodium, total and direct bilirubin, protein, uric acid, and GGT.
 3. Fasting glucose and insulin level for HOMA-IR
 4. Lipid panel
 5. Glycosylated hemoglobin
 6. Urine pregnancy test (only for women of childbearing potential).

7. Serum and plasma samples for non-invasive biomarkers related to liver injury pathophysiology and/or TLR-4 pathway
8. ELF™ test—Subjects must be an a fasted state prior to the sample collection
9. FibroSURE/ FibroMAX/ FibroTest—Subject must be in a fasted state prior to the sample collection
10. Additional blood sample needs to be collected for pharmacokinetic study.
 - Counsel subjects on weight loss, diet and exercise
 - Record any adverse events occurring after signing of the informed consent form
 - Record all medications that the subject has taken since prior visit
 - Dispense study drug

10.3.3.1 PK Substudy Subjects Only: From volunteered subjects for intensive pharmacokinetic studies: Blood samples will be obtained *prior to 12 hour dosing* (predose and at 0.25, 0.5, 0.75, 1.0, 1.5, 2.0, 3.0, 4.0, 6.0, 8.0, 10, 12, and 24 (next day) hours post dose administration in three volunteered subjects from each treatment group (5 mg and 10 mg bid). Additional pre-dose blood sample for trough PK level at Day 1, weeks 8, 16, and 24 will be collected for assessment of steady state PK analysis as well as biomarker study.

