#### **6.3.3 Safety Population**

The Safety Population includes all subjects who received at least one dose of study medication. Only subjects with clear documentation that no study medication was received may be excluded. In the event of treatment allocation errors, subjects will be analyzed for safety according to the treatment group they received.

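### The steady-state trough summary has no on-treatment condition and sets NQ values to zero, so subjects who have stopped drug but still attend lower the mean and make the geometric statistics non-computable

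*SAP*

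**What the plan says.** Population and NQ rule. SAP 6.10.3 states: "Trough (pre-dose) concentrations at Week 8, Week 16, and Week 24 will be summarized by treatment group for the Safety Population". It then sets the rule for non-quantifiable values: "If any trough concentration is NQ, it will be set to zero prior to summarization". Mean troughs by visit are also to be plotted for each treatment.

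Who is in that population. SAP 6.3.3: "The Safety Population includes all subjects who received at least one dose of study medication". Nothing there depends on whether the subject is still dosing when the sample is drawn. The exclusion for dosing deviations in SAP 6.3.5 applies only to the PK Substudy Population, which is planned as three volunteers per active dose.

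Which statistics. The opening of SAP 6.10.3 reads: "PK concentration data will be summarized for each time point using descriptive statistics from the Safety Population and PK Substudy Population". The list attached to that sentence includes the geometric mean and the geometric %CV.

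What the samples are for. Protocol 10.3.3, in the PK substudy paragraph, says that pre-dose samples at "weeks 8, 16, and 24 will be collected for assessment of steady state PK analysis". SAP 6.10.1 gives the same purpose. The footnote to the visit table in Protocol 10.2 extends the trough sample at these three visits to all patients.

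Who attends. Protocol 10.1: "Subjects should undergo all tests and evaluations specified in the protocol, regardless of whether they remain on study drug". Protocol 6.1 says that subjects with an adverse reaction "will discontinue study drug but will continue to complete all protocol-specified follow-up visits, assessments and evaluations". Protocol 10.4.4 asks sites to bring back subjects who have stopped treatment for the Week 24 procedures, and the PK sample is one of those procedures.

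**The concern.** A trough describes steady state only if the subject has been dosing. A subject who stopped weeks earlier and still comes to the visit gives a sample that is probably NQ. The SAP turns it into zero and averages it with the samples of subjects who are dosing. The resulting mean mixes exposure on drug with the proportion of subjects who have stopped.

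Intensive sampling is on Day 1 only, so these troughs are the trial's only repeated-dose exposure data. The PK profile and a recommended dose for later studies are secondary objectives. If the number of off-drug attenders differs between arms or grows over time, the table and the plot can suggest a dose or time pattern that comes from discontinuation and not from pharmacokinetics. The listed geometric statistics may also be unavailable, or may be computed on a subset that nobody has specified.

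**Working it through.** The plan gives no figure for troughs, so there is nothing to reproduce.

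Inputs:
- n = 20 subjects per arm (SAP 6.1).
- An NQ trough counts as 0, in the Safety Population (SAP 6.10.3 and 6.3.3).
- d = number of subjects in an arm who are off drug, attend and are NQ. The documents give no discontinuation rate. SAP 6.1 says only that sample size was not adjusted for dropouts. Assumed range: d = 1 to 6, or a rate p of 5% to 30%.
- On-drug troughs assumed lognormal with a nominal CV of 50% (no CV is given). The achieved CV in an arm of 20 is about 48%.

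**Arithmetic mean.** Mean(all) = mean(on drug) x (20 - d)/20.

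**CV.** With m = 20 - d and on-drug coefficient of variation c, CV(all)^2 = [m + (m - 1)c^2 - m^2/20]/19 x (20/m)^2. For d = 4 and c = 0.48: [16 + 15 x 0.2304 - 12.8]/19 x 1.5625 = 0.547, so the CV is 74%.

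| d | Mean / on-drug mean | Median / on-drug mean | Reported CV |
|---|---|---|---|
| 0 | 1.00 | 0.90 | 48% |
| 1 | 0.95 | 0.87 | 54% |
| 2 | 0.90 | 0.84 | 61% |
| 4 | 0.80 | 0.78 | 74% |
| 6 | 0.70 | 0.69 | 87% |

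The median is moved less than the mean, but it is not protected.

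**Geometric statistics.** The geometric mean is exp(mean of log x). One zero makes log x undefined, so neither the geometric mean nor the geometric %CV can be computed. The product form returns 0, which says nothing. If software drops the zeros, the arithmetic and geometric means describe different subjects. The chance of at least one zero in an arm is 1 - (1 - p)^20:
- p = 5%: 1 - 0.95^20 = 64%
- p = 10%: 1 - 0.90^20 = 88%
- p = 20%: 1 - 0.80^20 = 99%

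The chance that both active arms avoid a zero is 0.95^40 = 13% at p = 5% and 0.90^40 = 1.5% at p = 10%.

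**Illustration with assumed counts.** Suppose 1 of 20 are off drug on 5 mg and 5 of 20 on 10 mg. A true trough ratio of 2.0 is then reported as 2.0 x 0.75/0.95 = 1.58. If one arm goes from 1 to 5 off drug between Week 8 and Week 24, the mean trough falls to 0.75/0.95 = 0.79 of its Week 8 value with no change in PK.

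**Comparison within the SAP.** For the intensive profiles, SAP 6.10.2 sets NQ values after the last measurable concentration to missing. No reason is given for using zero for troughs.

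**After restriction to on-treatment samples.** The mean returns to 1.00 of the on-drug mean at every d. The geometric mean becomes computable, at 0.96, 0.90 and 0.80 of the arithmetic mean for a nominal CV of 30%, 50% and 80%, provided that no on-drug trough is itself NQ.

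**The case against.** Five points can be made for the plan.

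1. Not every subject who stops becomes a zero. Protocol 10.4.6 sends early discontinuers to an end-of-treatment visit with follow-up 4 weeks later, and 10.8 places that visit at the time of withdrawal. Protocol 6.3 and 12.4 withdraw some subjects for ALT rises. These subjects give no later Week 8 or 16 trough, and a sample near the last dose may still be quantifiable. This stands and limits d. It does not remove the problem, because 6.1, 10.1 and 10.4.4 point the other way for subjects who stop drug and stay in the study. A low quantifiable value from a recent stopper also lowers the mean.

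2. The term pre-dose can be read as excluding anyone with no dose to follow. That is a reasonable reading, but no rule says so, and Protocol 10.1 asks for all tests whatever the drug status.

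3. The trough paragraph names no statistics. The geometric mean comes from the general opening of 6.10.3. That sentence covers each time point in the Safety Population, and the scheduled samples for all subjects are Day 1 pre-dose and the three trough visits, so applying it to the troughs is the natural reading.

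4. Minimum, median and individual plots are planned, so zeros would be visible. They would be seen, but not separated into off-drug and on-drug NQ values.

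5. A reader might infer that the zeros also corrupt the exposure/ALT correlation in Protocol 11.3. The documents do not support this. The zero rule applies to the summary, Protocol 11.3 sets no NQ rule, and SAP 6.10.3 says only that PK and efficacy may be explored. For that purpose a near-zero concentration is the true exposure of an off-drug subject. Removing it would condition on adherence after randomisation and could add bias.

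**Conclusion.** The point holds for the descriptive trough summary and the mean-trough plots. Followed as written, the SAP counts off-drug NQ samples as zeros in a summary meant for steady state. The arm mean is multiplied by (20 - d)/20, from 0.95 to 0.70 for an assumed d of 1 to 6, and a single zero defeats the geometric mean and geometric %CV on the log scale. The multiplier is exact given d. The value of d is an assumption and counts only subjects who have stopped, still attend and are NQ.

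A reader might go further and predict a specific loss of dose proportionality or a falling trough over time. The 1.58 ratio and the 21% fall only show what unequal counts would do; the documents give no rate, no assay limit and no half-life from which to predict them. No hypothesis test depends on this summary and the primary MRI analysis is unaffected. It should be corrected because it bears on a secondary objective and the correction is cheap.

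**What to change.** Amend SAP 6.10.3 as follows:

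- Restrict the trough summary and the mean-trough plots to JKB-121 samples taken while the subject is on treatment. Flag these from the last-dose and interruption dates that SAP 6.8 already uses for exposure. Where the last-dose date is missing, SAP 6.8 substitutes the completion or termination date. The flag should not use that substitute, because it would mark an off-drug attender as dosing; list such samples as undetermined.
- Add a time-since-dose window only if dose times are recorded. Protocol 9.5 provides paper diaries and bases compliance on pill counts, but does not say that clock times are captured.
- List off-drug samples separately. Placebo samples, if assayed, should be near-uniformly NQ and do not belong in the summary.
- For on-treatment NQ values, report their number and pre-specify a non-zero convention for the geometric statistics, for example half the lower limit of quantification (LLOQ/2). Alternatively, report the median with the NQ count.
- State that the exposure/ALT exploration keeps off-drug concentrations, with its own NQ rule.

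The cost is SAP wording and one dataset flag, with no new data collection unless a time window is wanted. The downside is fewer trough values in the summary.
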